**4. ESTIMATED DURATION OF THE STUDY**

4 years

**5. LAY LANGUAGE SUMMARY OR SYNOPSIS (no more than one paragraph)**

We would like to know if the use of vaginally applied estrogen can prevent the problem of repeated urinary tract infections (UTI) in women who have gone through menopause. We will use two forms of vaginal estrogen that are available by prescription (a ring and a cream) and compare their efficacy to that of a commercially available cream without any active ingredient. We are going to look at if the vaginal estrogen can prevent UTIs altogether and also the number of UTIs each group experiences over a 6 month period. After 6 months, all subjects will receive vaginal estrogen and the women will be able to choose which form of vaginal estrogen (ring or cream) they would like to use. We will then be able to compare the number of UTIs on and off active vaginal estrogen treatment within those subjects who started on the cream without estrogen. We are also going to look at quality of life before and during treatment using questionnaires and whether subjects stop using the treatments or do not use them as directed (compliance). Additionally, urine and vaginal swab specimens will be collected and processed for bacterial 16s rRNA characterization at baseline and after treatment.

**6. SPECIFIC AIMS**

*Primary Objective*

The primary purpose of this study is to assess the efficacy of vaginal estrogen versus placebo at 6 months on the prevention of urinary tract infections (UTI) in postmenopausal women with history of recurrent UTI.

*Secondary Objectives*

- [1] a] To assess overall rates of UTI over 6 months in postmenopausal women with history of recurrent UTI receiving vaginal estrogen (ring or cream).
- b] To compare rates of UTI between 6 and 12 months of those subjects initially randomized to placebo.
- [2] To assess the impact of treatment of recurrent UTI with vaginal estrogen on quality of life at 6 and 12 months in postmenopausal women with history of recurrent UTI.
- [3] To assess compliance with vaginal estrogen (ring or cream) treatment at 12 months in postmenopausal women with history of recurrent UTI.
- [4] To assess efficacy of vaginal estrogen at 12 months in those compliant with treatment.

*Primary Hypothesis*

Vaginal estrogen (ring and cream) will be superior to placebo in the prevention of UTI at 6 months of treatment in postmenopausal women with a history of recurrent UTI.

*Secondary Hypotheses*

- [1] a] Overall rates of UTI in the first 6 month period in those women receiving vaginal estrogen will be

lower compared to those receiving placebo.

b) Rates of UTI will decrease between 6 and 12 months for those initially on placebo and subsequently using estrogen.

[2] Vaginal estrogen will result in improved QOL in postmenopausal women with history of recurrent UTI.

a) compared to placebo at 6 months.

b) compared to baseline at 12 months.

[3] Adherence with vaginal ring will be superior to cream.

[4] At 6 and 12 months, vaginal estrogen will be effective at preventing UTI in those adherent to therapy.

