### **Overall Design**

This is an investigator initiated, multicenter, single blind, randomized placebo controlled trial of vaginal estrogen (delivered by ring or cream) compared to placebo control. During the blinded portion, subjects will be randomized to either receive vaginal estrogen (via ring or cream), or receive a placebo cream. Conjugated estrogen cream at a strength of 0.625mg/g and a dose of 0.5g (0.312 mg) twice a week will be used, as will estradiol ring containing 2mg of estradiol placed vaginally every 3 months. These two doses are standard clinical dosing based on FDA approved treatment of vaginal atrophy and result in similar vaginal effects. The placebo cream will be a commercially available over the counter oil based vaginal lubricant which is semi-solid at room temperature and contains no active ingredients. Primary outcome will be assessed at 6 months with vaginal estrogen group compared to the placebo control. However, in order to improve recruitment and assess long term compliance, satisfaction and efficacy in the as treated groups, we will offer open label use of ring or active cream after 6 months of blinded treatment. Those on placebo at 6 months will be allowed to choose which vaginal estrogen form (ring or cream) she would like to use for another 6 months and secondary outcomes captured after their 6 months of active treatment will be combined with those 6 month measures collected from those originally randomized to active therapy. Vaginal estrogen group will also be allowed to choose which administration (ring or cream) they would like to continue with at 6 months. Subjects will not be told which preparation is the placebo in order for them to remain blinded to treatment. Providers, however, will not be blind to this. We chose not to use a placebo ring, as we felt this could be a nidus for infection skewing the results and unnecessarily placing subjects at risk. We will attempt to minimize bias by having providers blinded to outcome measures and questionnaire responses.

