The primary outcome is occurrence of one or more symptomatic UTIs within 6 months of treatment. Subjects will perform a clean catch for a urine culture when they have symptoms of a UTI using the CDC definition of symptoms, as above. If the subject cannot perform a clean catch themselves, a provider may obtain a catheterized specimen as clinically indicated, in which case the threshold for bacterial count will decrease to  $10^3$  microorganisms per mL. Secondary outcomes include assessing rate of UTI over the course of the year in those women who received placebo and then vaginal estrogen, as well as comparing the rates of UTI in the placebo and vaginal estrogen group. Quality of life (QOL) questionnaires will be administered at baseline, at the end of randomization and at drop out or 12 months. There are no validated questionnaires that assess UTI specifically, therefore we have chosen questionnaires which relate to general QOL, as well as those which include symptoms similar to that of UTI. In addition, we know that vaginal estrogen can treat dyspareunia, so we will capture sexual function. We will be using the SF 12, as well as the overactive bladder satisfaction questionnaire (OAB-SAT-q), the medical, epidemiological and social aspects of aging questionnaire (MESA), the urogenital distress inventory (UDI-6) and the female sexual function index (FSFI) along with the patient satisfaction global ratings: patient satisfaction question (PSQ), estimated percent improvement (EPI) and global perception of improvement (GPI). The SF 12 is a general quality of life questionnaire initially used to survey health status [26]. The OAB-SAT-q is a questionnaire evaluating satisfaction pertaining to overactive bladder symptom treatment, symptoms which are similar to those of a UTI [27]. The MESA questionnaire explores lower urinary tract symptoms [28]. The UDI-6 is the short form of the urogenital distress inventory which surveys life impact and symptom distress of urinary incontinence and related issues in women [29]. The FSFI is a validated questionnaire assessing female sexual function [30]. The PSQ, EPI and GPI are patient global ratings, satisfaction, perception of improvement and estimated percent improvement validated previously in the treatment of urinary incontinence [31]. These questionnaires will allow us to assess whether general quality of life, irritative urinary symptoms, as well as sexual function are improved by vaginal estrogen, which could occur secondary to the correction of atrophic vaginitis alone. We will also assess whether QOL changes when UTIs occur with less frequency and will assess overall patient satisfaction with treatment. We will also be evaluating adherence in each treatment arm. Adherence with creams will be assessed by medication diary and weighing the tubes at each 3 month visit and vaginal rings will be accounted for by confirming that the ring is still in place in the vagina and then exchanging it for the new ring. Adherence is defined as  $\geq 80\%$  usage.

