
The open label portion of the study will start at month 6. All of those women using placebo cream will be allowed to choose a vaginal estrogen preparation to use for the remainder of the study (ring or cream). Those women initially randomized to vaginal estrogen will be allowed to choose which vaginal estrogen preparation they want to continue with. The rationale behind an open label portion of the study is an incentive to participate. Vaginal estrogen is available to patients via prescription, as an off label indication, but coverage for this therapy can be limited and treatment costly (up to \$300 per prescription refill). The open label portion of the study should provide incentive for women to enroll when the study drug is already available, as will modest reimbursement for study visits. We will also be able to compare the rates of UTI in those women who received placebo initially to their rate of UTI on drug.

Eligible women will be consented and block randomized using preset, opaque and sealed envelopes. These cards will either say “study drug 1, 2 or 3” and will be placed in numbered envelopes in a random order and selected by study staff and dispensed to the subject. These drugs will be stored in a locked cabinet in the Female Pelvic Medicine clinic. After the subject receives her study drug, she will receive administration instructions. If the assigned treatment is a ring, the subject will have it placed by the provider, if it is a cream, the cream will be weighed at baseline and she will be shown how to place it vaginally herself and instructed on bringing the remaining study drug to each 3 month visit for weighing.

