**Methodology**  
*Details of the Intervention*

Women will be randomized to one of the two vaginal estrogen arms or placebo in a 1:1:2 fashion. For those randomized to the ring, the ring will be placed by the provider in 3 month intervals at their visits. Subjects randomized to cream arm will receive 0.5g (0.312 mg) conjugated estrogen vaginal cream per vagina at bedtime two times per week. The placebo cream will be administered in a similar fashion. These cream tubes will be weighed at baseline and again at the every 3 month office visits to assess adherence. They will also be given diaries to keep track of their medication administration. Subjects will be called once a month for the first 3 months by study personnel to assess for adverse events as well as UTI symptoms. After the first 3 months, a relationship will be established with study personnel and the participants will be encouraged to call with symptoms.

Written quality of life questionnaires will be administered at baseline, at the end of randomization or 6 months and at drop out (if possible) or 12 months. The questionnaires include the OAB-SAT-q, MESA, UDI-6, FSFI and PSQ, GPI and EPI rating scales and are previously validated questionnaires referenced above in *Overall Design* [26-31]. These will assess global QOL, as well as irritative bladder symptoms and sexual function. We will also collect baseline data with respect to medical history and concomitant pelvic medicine diagnoses.

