### ***Safety and Toxicity Measures***

If subjects in any arm develop 3 UTIs in the 6 month treatment period, they will be unblinded. If on placebo, they will be provided active study drug as would have been done at the 6 month visit or if they are on study drug, they will be treated according to the provider's clinical practice and their outcomes recorded for the remainder of the study. Six month outcome assessments will be administered early to capture QOL data for the secondary analyses. We will also be monitoring for adverse events monthly with phone calls for the first 3 months, specifically querying symptoms of pain, bleeding or abnormal discharge which would prompt evaluation for relatedness to study participation. Events related to participation will not be billed to insurance, however, any events which are part of routine clinical care (ie. UTI or other pelvic floor disorder treatment such as urinary incontinence) will be billed according to standard clinical care. After that subjects will be encouraged to call with any adverse reactions. Attribution of these events to study participation will be assigned by the investigator and reported to the IRB according to local policy.

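### Hypothesis 1b is a within-woman comparison (UTI rate off versus on estrogen in placebo starters), but the only method named for UTI counts compares groups and does not test it

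*Combined protocol and SAP*

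**What the plan says.** **The comparison promised.** Section 6 (Specific Aims), secondary hypothesis 1b: "Rates of UTI will decrease between 6 and 12 months for those initially on placebo and subsequently using estrogen". Read alone, this could mean a trend inside months 6-12. Two other places settle the meaning:

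- The lay summary (section 5) says the study will "compare the number of UTIs on and off active vaginal estrogen treatment within those subjects who started on the cream without estrogen".
- Overall Design, on the open-label portion, says it will "compare the rates of UTI in those women who received placebo initially to their rate of UTI on drug".

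Overall Design also lists as a secondary outcome "assessing rate of UTI over the course of the year in those women who received placebo and then vaginal estrogen".

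**The methods offered.** The Data Analysis section assigns UTI counts, in both the randomized and the follow-up period, to a Poisson model that compares groups. It gives paired t-tests to quality of life, baseline against month 12, in an active treatment group. It gives random-effects models to variables measured on at least three occasions, without listing those variables.

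**The early switch.** Under Safety and Toxicity Measures, a woman with three UTIs in the 6-month treatment period is unblinded. "If on placebo, they will be provided active study drug as would have been done at the 6 month visit". The same paragraph adds: "Six month outcome assessments will be administered early to capture QOL data for the secondary analyses". It does not say how her UTI counts are divided between the two periods.

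**The concern.** The plan commits to a question about change within women and then names, for that outcome, a method that answers a question about difference between arms. An analyst who follows the text literally produces a months 6-12 comparison that carries no information on 1b. An analyst who sees the mismatch must choose an estimator and a period boundary, possibly after seeing the data.

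The choice matters because of the early switch. A placebo woman who reaches her third UTI quickly has a short off-drug period with a high count, and the period ends because of that count. Under some common estimators her before rate is inflated, so her rate appears to fall after the switch even if the drug does nothing. With about 20 women and no stated estimator, a reader could not tell whether the choice came before the data.

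**Working it through.** **1. Inputs.** From Sample Size Consideration: 63% of placebo women and 16% of active women have at least one UTI in 6 months; 20 women per group at the end of the randomized period; two-sided 0.05. The plan gives no power or sample size for 1b. Its primary figure reproduces: exact Fisher power at 20 per group is 82.3%, against the stated 80%.

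**2. Convert to rates (Poisson assumption).** Mean per 6 months = −ln(1 − p).

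- Placebo: −ln(0.37) = 0.994.
- Estrogen: −ln(0.84) = 0.174.
- Implied on/off ratio: 0.174/0.994 = 0.175.

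**3. The named model in months 6-12.** Every woman is offered estrogen from month 6.

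- Estrogen works as assumed: 0.174/0.174 = 1.
- Estrogen does nothing: 0.994/0.994 = 1.

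The expected ratio is 1 in both cases, so the comparison cannot tell 1b true from 1b false.

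**4. Share switching early.** P(3 or more UTIs in 6 months) = 1 − 0.37 × (1 + 0.994 + 0.994²/2) = 1 − 0.37 × 2.488 = 0.079. This is about 8%, or 1.6 of 20 women.

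**5. Inert drug, true ratio 1, split at actual estrogen start.** Let λ = 0.994 and take 6 months as the time unit.

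- *Averaged individual rates.* A woman who does not switch contributes her count. A woman who switches at time t contributes 3/t. Integrating over the time of the third event, the expected before rate is λ[1 + ½P(N ≥ 2)], with P(N ≥ 2) = 1 − 0.37 × 1.994 = 0.262. The after rate is λ. Ratio = 1/(1 + 0.131) = 0.88.
- *Conditional Poisson, woman by woman.* Simulation of 2,000,000 women gives 0.94 with follow-up to month 12, or 0.96 if only the next 6 months count as after.
- *Pooled person-time.* Expected events off drug equal λ times expected time off drug, even though the stopping time depends on the events. Ratio 1.00.
- *Calendar split at month 6.* Both halves have mean λ. Ratio 1.00.

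**6. Size against noise.** With 20 women followed to month 12, the conditional Poisson log ratio has a standard deviation of about 0.36 under an inert drug. The bias is ln(0.944) = −0.06, so about 0.06/0.36, or one sixth of a standard deviation.

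**7. Can 1b be answered?** Take two equal 6-month periods, means 0.994 and 0.174, and an exact two-sided test of the after count given the total (binomial, ½ under no change). Enumerated power is 93%, 85% and 71% with 20, 16 and 12 women followed to month 12. The lower two numbers are assumed, since the plan's 20 refers to the end of the randomized period.

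**The case against.** The strongest reply is that the plan does contain a usable method. Visits are every 3 months, and the safety monitoring section reviews data quarterly, including each woman's number of UTIs. Counts are therefore looked at on more than three occasions, and a random-effects model of them would be a within-woman analysis close to what is wanted. This stands in part. A reader might infer that no stated analysis could ever bear on 1b, and that is too strong. But the quarterly review is a monitoring activity, and the random-effects sentence names neither UTI counts nor an off/on contrast. The one sentence that does name counts sends them to the between-group model.

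Second, the period boundary is not fully open. The lay summary and Overall Design speak of rates on and off drug, which points to a split at actual estrogen start. This is accepted and shapes the fix. What remains unstated is how counts and time at risk are handled for women who switch early.

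Third, the bias is small at the plan's own rates, and the largest figure belongs to an estimator the plan never mentions. This is also accepted: the early switch is a reason to state the estimator, not evidence that 1b would be misleading.

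A reader might also infer that the pooling in Overall Design, where outcomes "captured after their 6 months of active treatment will be combined with those 6 month measures collected from those originally randomized to active therapy", is the intended test of 1b and would mix 1a into it. The documents do not support that. The pooling is described for secondary outcomes generally, and no passage makes it the test of 1b.

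**Conclusion.** The point holds. Hypothesis 1b is a within-woman comparison, the only method named for UTI counts compares groups, and in months 6-12 that comparison has an expected ratio of 1 whatever the truth of 1b. This conclusion comes from reading the sections together and, provided estrogen acts alike in both arms, does not depend on the event rates.

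The secondary finding is quantitative and modest. With Poisson counts at 63%, an inert drug can show anything from no change to a fall of about 12%, depending on how early switchers are handled. That is small beside the sampling error with about 20 women and beside the implied true ratio of 0.175. Overdispersed counts would change these figures, and the plan gives no dispersion.

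Even when well analysed, 1b is a before/after contrast without a concurrent control, with open-label drug in the second period. Ascertainment also differs: women are "called once a month for the first 3 months by study personnel to assess for adverse events as well as UTI symptoms" and thereafter are encouraged to call, so scheduled symptom calls fall only in the off-drug half for placebo starters. The primary analysis and hypothesis 1a are unaffected. This should be corrected, but it does not threaten the trial's main conclusion.

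**What to change.** In the Data Analysis section, add a sentence for 1b that states:

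- **Population and model:** women randomized to placebo; a within-woman count model, for example a Poisson or negative binomial mixed model, with period (off versus on estrogen) as the contrast and log person-time as offset.
- **Primary split:** at actual estrogen start, in line with the lay summary and Overall Design.
- **Sensitivity analysis:** the calendar split at month 6. It is unbiased under no effect, but slightly dilutes a true effect (0.175 becomes about 0.18 at the plan's rates).
- **Exclusion:** the months 6-12 comparison between randomized arms is not the test of 1b.
- **Reporting:** 1b is uncontrolled, supportive evidence, with the change in symptom calls after month 3 noted.

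**Cost.** Plan wording and a little more analysis, plus the date of each UTI and of estrogen start. Enrollment is complete, and nothing in trial conduct changes. The mixed model relies on its random-effect distribution, and in simulation its likelihood-ratio test rejected in about 6% of null trials with 12 to 20 women. Power is limited if few women reach month 12: the exact-test figures of 93%, 85% and 71% are a guide, not the power of the mixed model itself.

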## **7. BACKGROUND AND SIGNIFICANCE**

### *Recurrent Urinary Tract Infection*

Recurrent urinary tract infection (UTI) in postmenopausal women is common, negatively affects the quality of life for millions and has significant impact on health care delivery [1]. The annual social cost of UTIs has been estimated at 1.6 billion dollars with 11.3 million prescriptions written for treatment [2]. Up to 15% of women over 60 will develop frequent UTIs [3]. This number increases to 20% over the age of 65 and between 25-50% of patients 80 years of age and older experience bacteruria [4]. Recurrent UTI is defined as three or more UTIs in 12 months or two UTIs in 6 months [5]. The pathogenesis of recurrent UTI in postmenopausal women may in part be related to the declining levels of systemic estrogen after menopause. This change causes differences in the bacterial flora of the vagina due to increasing vaginal pH, resulting in colonization by uropathogens (escherichia coli and enterococcus) as opposed to the normal lactobacillus flora seen in premenopausal women. While not entirely clear, the general consensus is that this vaginal colonization with enteric bacteria leads to more frequent UTIs [6]. Thus, a common therapy for prevention of recurrent UTI is topical vaginal estrogen. While commonly used in practice, there is a paucity of data on the efficacy of vaginal estrogen for the prevention of recurrent UTI in currently prescribed vehicles and doses.

### *Vaginal Estrogen*

There are a number of modes of delivery for vaginal estrogen (full and low dose) such as tablets (Vagifem™), creams (Estrace™ and Premarin™) and vaginal rings (Estring™ and Femring™). After safety concerns raised by the Women's Health Initiative, use of hormones is a concern for both patients and practitioners regarding the use of these compounds by any method. As such, the goals of treatment with hormones are to identify the minimum dose of therapy needed to achieve benefit. Given concerns regarding systemic hormone replacement therapy (HRT), topical dosing has become the mainstay of local therapy for vaginal atrophy/dyspareunia. Vagifem™, Estring™, Estrace™ and Premarin™ cream have been FDA approved for the treatment of atrophic vulva, atrophy of the vagina, urethral atrophy [7]. Circulating levels of estradiol have been shown to be minimal with low dose vaginal estrogen creams, tablets and the estrogen ring [6, 8]. Thus, systemic effects from these low dose topical therapies are felt to be extremely low. With the estrogen ring, serum estradiol increased from a baseline of 16+22 pmol/l to 49+64 pmol/l at week 24, then fell to 20+19 pmol/l by week 48 [10]. With administration of 0.5g twice weekly, serum estradiol increased from a baseline of 15+33 pmol/l to 36+51 pmol/l at week 24 and remained there at week 48 [10]. These levels are substantially than the upper limit of normal (130 pmol/l) for postmenopausal women. The other concern with any unopposed estrogen is endometrial safety. There have been several large studies that have established endometrial safety of various low-dose formulations of vaginal estrogen (Vagifem™, Estring™ and conjugated estrogen cream at a dose of 0.3mg) [9-11]. Controlled studies of more than 1,000 women on unopposed estrogen ring and estrogen cream at doses proposed in this study have not identified any endometrial cancers. With low systemic absorption and no significant increase in endometrial pathology with low dose vaginal estrogen, it is generally thought that the use of progestins is not necessary to protect the endometrium [12]. Additionally, because systemic absorption is minimal, it can be assumed that there should not be an effect on patients with breast cancer, however, the data is limited [13]. Topical, low dose vaginal estrogen is in general well tolerated, with dropout rates of 7 and 8% in prior studies with the ring and cream respectively. Only reported adverse events significantly higher than placebo was breast pain, however, the incidence of this is low [13]. Other reported adverse events in uncontrolled observational studies include vaginal bleeding, which occurred rarely in one study, however, endometrial sampling in those women with vaginal bleeding revealed no evidence of hyperplasia or malignancy [14].

While no formulation of vaginal estrogen is approved for prevention of UTIs, it is commonly used “off label”. The theory is that recurrent UTIs in postmenopausal women are directly a result of vaginal atrophy. The hypothesis behind its efficacy involves re-estrogenizing the vaginal mucosa, although it does not lead to premenopausal circulating levels of estradiol, leads to local effects on the balance of bacterial flora mimicking premenopausal states. In premenopausal women, the vagina is colonized by lactobacilli which result in a low vaginal pH and inhibits overgrowth of other bacteria. In postmenopausal states the vaginal pH is increased which allows overgrowth of pathogens. Previous trials with vaginal estrogen have shown that vaginal estrogen administration changes the pH of the vagina to premenopausal states, resulting in restoration of the bacterial balance [15]. However, this study examined higher doses of estrogen cream (0.5mg daily for 2 weeks followed by twice a week, as opposed to current dosing of 0.3125 mg twice a week) and only explored one preparation.

